4.1 Potential Adverse Events

The following anticipated adverse events have been identified as possible complications of percutaneous atrial fibrillation ablation procedures in general as well as with the FARAPULSE Endocardial Multi Ablation System:

- Access site complications (e.g., hematoma, pseudo-aneurysm, laceration, bleeding) potentially requiring surgical intervention
- Air embolism
- Allergic reaction or fever resulting from contact with catheters
- Anemia
- Arrhythmia, potentially requiring cardioversion, defibrillation, or rhythm management device
- Arteriovenous fistulae
- Back pain
- Bed sores
- Bleeding, hematoma, hemorrhage or aneurysm at vascular access sites
- Blood pressure changes including hypotension or hypertension
- Coronary artery or vein injury
- Cardiac tamponade or perforation
- Cardiac arrest or cardiac failure
- Catheter entrapment
- Cardiogenic shock
- Conduction system injury resulting in sinus arrest or heart block, either transient or permanent, potentially requiring pacemaker insertion
- Congestive heart failure
- Death
- Drug allergic reaction or side effects (e.g., from contrast, steroids, analgesics, anesthetics, anticoagulants, sedatives, etc.)
- Embolism due to presence of thrombus or introduction of air
- Esophageal injury, ulcer or fistula
- Hemorrhage
- Hemodynamic compromise
- Hemopericardium
- Hemoperitoneum
- Hemothorax
- Local infection, systemic infection, and/or sepsis
- Muscle contractions due to electric stimulation
- Myocardial infarction / transient ischemia

- Nerve damage
- Organ failure
- Pain
- Perforation (e.g., of diaphragm, liver, lung, and/or vessels).
- Pericardial irritation
- Pericardial effusion
- Pericarditis
- Peritonitis
- Phrenic nerve injury with paralysis of the diaphragm and breathing impairment
- Pneumomediastinum
- Pneumopericardium
- Pneumoperitoneum
- Pneumothorax
- Pulmonary vein injury or stenosis
- Risk of cancer or birth defect/harm to fetus from x-ray exposure
- Skin burns/irritation from x-ray exposure
- Stroke/transient ischemic attack
- Surgical procedure to remove retained catheter
- Thrombosis
- Vessel damage, dissection, or occlusion.

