6.1 Primary Safety Endpoint

The primary safety endpoint for this study is the Composite Safety Endpoint (CSE) defined as the incidence of the following early-onset and late-onset serious adverse events (SAEs) which are device- or procedure-related, as adjudicated by the CEDMC and defined below in **Table 4. Composite Safety Endpoint Definitions**.

Early onset (within 30 days of an Index or Remap Procedure)

- Death
- Myocardial infarction (MI)
- Persistent diaphragmatic paralysis
- Stroke or transient ischemic attack (TIA)
- Peripheral or organ thromboembolism
- Pericarditis
- Cardiac tamponade / perforation
- Vascular access complications requiring intervention
- Heart block

Late onset (any time during follow-up through 12 months)

- Pulmonary vein (PV) stenosis (> 70% diameter reduction from baseline)
- Atrio-esophageal fistula

Table 4. Composite Safety Endpoint Definitions

Adverse Event	Description/Criteria
Death	Death
Myocardial infarction (MI)	Myocardial infarction will be demonstrated by any one of the following: 1) detection of ECG changes indicative of new ischemia (new ST-T wave changes or new LBB) that persist for more than 1 hour. 2) development of new pathological Q waves on an ECG 3) imaging evidence of new loss of viable myocardium or new regional wall motion abnormality
Persistent diaphragmatic paralysis	Diaphragmatic paralysis: Change from baseline diaphragmatic function as demonstrated radiographically by elevation of the diaphragm above the normal range but not due to a pulmonary process such as atelectasis. Permanent: not resolved by completion of study follow-up
Stroke or transient ischemic attack (TIA)	Stroke is an acute symptomatic episode of neurological dysfunction attributed to a vascular cause (ischemia or hemorrhage) in which symptoms last more than 24 hours, or if symptoms last less than 24 hours, a brain imaging study demonstrates infarction. Transient ischemic attack is a new focal neurological deficit with rapid symptom resolution always within 24 hours.

Adverse Event	Description/Criteria
Peripheral or organ thromboembolism	Formation in a blood vessel of a clot (thrombus) that results from the breaking loose of all or part of an existing thrombus, which is then carried by the blood to lodge in/occlude a more distal vascular site.

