Pericarditis	Inflammation of the pericardial space that results in an effusion that leads to hemodynamic compromise or required pericardiocentesis, prolongs hospitalization by more than 48 hours, requires hospitalization, or persists for more than 30 days following the ablation procedure.
Cardiac tamponade/perforation	The development of a significant pericardial effusion during or within 30 days of undergoing the index AF ablation procedure. A significant pericardial effusion is one which results in hemodynamic compromised (<80mmHg systolic bp), requires elective or urgent pericardiocentesis, or results in a 1cm or more pericardial effusion as documented by echocardiography.
Vascular access complications requiring intervention	Vascular access complication (e.g. groin hematoma, AV fistula, pseudoaneurysm) requiring intervention (e.g. surgical repair, blood transfusion).
Heart block	Impairment of AV conduction requiring permanent pacing intervention, if resulting from inappropriate ablation application.
Pulmonary vein (PV) stenosis	>70% diameter reduction of pulmonary vein from baseline CT/MRA scan.
Atrio-esophageal fistula	Connection between the atrium and the lumen of the esophagus as evidenced by documentation of esophageal erosion combined with evidence of a fistulous connection to the atrium.

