- the event has a temporal relationship with investigational device use/application or procedures;
- the event involves a body-site or organ that
- the investigational device or procedures are applied to;
- the investigational device or procedures have an effect on;
- the serious event follows a known response pattern to the medical device (if the response pattern is previously known);
- the discontinuation of medical device application (or reduction of the level of activation/exposure) and reintroduction of its use (or increase of the level of activation/exposure), impact on the serious event (when clinically feasible);

- other possible causes (e.g. an underlying or concurrent illness/ clinical condition or/and an effect of another device, drug or treatment) have been adequately ruled out;
- harm to the subject is due to error in use;
- In order to establish the relatedness, not all the criteria listed above might be met at the same time, depending on the type of device/procedures and the serious event.

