IF (30≤ (EVENT DATE-PROCEDURE DATE IN **PROCEDURAL DATA FORM (PR)**) **OR** (30≤ (EVENT DATE-REMAPPING DATE IN **FOLLOW-UP 3D ELECTROANATOMICAL MAPPING FORM (RM)**) **AND** PRIMARY SAFETY ENDPOINT EVENT CRITERIA=' CVA' **THEN** CVA='Yes'.
ELSE CVA='No'.

- Derived criteria "Major pericarditis" will be defined as follows:
IF (30≤ (EVENT DATE-PROCEDURE DATE IN **PROCEDURAL DATA FORM (PR)**) **OR** (30≤ (EVENT DATE-REMAPPING DATE IN **FOLLOW-UP 3D ELECTROANATOMICAL MAPPING FORM (RM)**) **AND** PRIMARY SAFETY ENDPOINT EVENT CRITERIA=' Major pericarditis' **THEN** Major pericarditis ='Yes'.
ELSE Major pericarditis ='No'.
- Derived criteria "Tamponade/Perforation" will be defined as follows:
IF (30≤ (EVENT DATE-PROCEDURE DATE IN **PROCEDURAL DATA FORM (PR)**) **OR** (30≤ (EVENT DATE-REMAPPING DATE IN **FOLLOW-UP 3D ELECTROANATOMICAL MAPPING FORM (RM)**) **AND** PRIMARY SAFETY ENDPOINT EVENT CRITERIA=' Tamponade/Perforation' **THEN** Tamponade/Perforation ='Yes'
ELSE Tamponade/Perforation ='No'.
- Derived criteria "Pneumothorax" will be defined as follows:
IF (30≤ (EVENT DATE-PROCEDURE DATE IN **PROCEDURAL DATA FORM (PR)**) **OR** (30≤ (EVENT DATE-REMAPPING DATE IN **FOLLOW-UP 3D ELECTROANATOMICAL MAPPING FORM (RM)**) **AND** PRIMARY SAFETY ENDPOINT EVENT CRITERIA=' Pneumothorax' **THEN** Pneumothorax ='Yes'
ELSE Pneumothorax ='No'
- Derived criteria "Heart Block" will be defined as follows:
IF (30≤ (EVENT DATE-PROCEDURE DATE IN **PROCEDURAL DATA FORM (PR)**) **OR** (30≤ (EVENT DATE-REMAPPING DATE IN **FOLLOW-UP 3D ELECTROANATOMICAL MAPPING FORM (RM)**) **AND** PRIMARY SAFETY ENDPOINT EVENT CRITERIA=' Heart Block' **THEN** Heart Block ='Yes'
ELSE Heart Block ='No'
- Derived criteria "Pulmonary Edema" will be defined as follows:
IF (30≤ (EVENT DATE-PROCEDURE DATE IN **PROCEDURAL DATA FORM (PR)**) **OR** (30≤ (EVENT DATE-REMAPPING DATE IN **FOLLOW-UP 3D ELECTROANATOMICAL MAPPING FORM (RM)**) **AND** PRIMARY SAFETY ENDPOINT EVENT CRITERIA=' Pulmonary Edema' **THEN** Pulmonary Edema ='Yes'
ELSE Pulmonary Edema ='No'
- Derived criteria "New or Prolonged Hospitalization, excl. AF/AFL" will be defined as follows:
IF (30≤ (EVENT DATE-PROCEDURE DATE IN **PROCEDURAL DATA FORM (PR)**) **OR** (30≤ (EVENT DATE-REMAPPING DATE IN **FOLLOW-UP 3D ELECTROANATOMICAL MAPPING FORM (RM)**) **AND** PRIMARY SAFETY ENDPOINT EVENT CRITERIA=' New or Prolonged Hospitalization, excl. AF/AFL' **THEN** New or Prolonged Hospitalization, excl. AF/AFL ='Yes'

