ELSE New or Prolonged Hospitalization, excl. AF/AFL ='No'

CONFIDENTIEL / CONFIDENTIAL

Toute reproduction ou distribution, totale ou partielle, de ce document, sans autorisation préalable de ICON PLC est interdite.
Reproduction and distribution of this document, in whole or in part, is strictly forbidden without prior authorization from ICON PLC.

	STATISTICAL ANALYSIS PLAN	FARAPULSE PersAFOne SAP V1.0 PERSAFONE Page 28 /49
---	----------------------------------	--

- Derived criteria “Vascular Access Complication” will be defined as follows:
IF (30≤ (EVENT DATE-PROCEDURE DATE IN PROCEDURAL DATA FORM (PR)) **OR** (30≤ (EVENT DATE-REMAPPING DATE IN FOLLOW-UP 3D ELECTROANATOMICAL MAPPING FORM (RM)) **AND** PRIMARY SAFETY ENDPOINT EVENT CRITERIA=’ Vascular Access Complication’ **THEN** Vascular Access Complication =’Yes’
ELSE Vascular Access Complication =’No’
- Derived criteria “Total Early and Late Onset Composite Safety Endpoint” will be defined as follows:
IF Death=Yes **OR** Myocardial infarction =Yes **OR** PV Stenosis =Yes **OR** Diaphragmatic Paralysis =Yes **OR** AE fistula =Yes **OR** TIA =Yes **OR** CVA=Yes **OR** Major pericarditis =Yes **OR** Tamponade/Perforation =Yes **OR** Pneumothorax =Yes **OR** Heart Block =Yes **OR** Pulmonary Edema =Yes **OR** New or Prolonged Hospitalization, excl. AF/AFL =Yes **OR** Vascular Access Complication =Yes **THEN** Total Early and Late Onset Composite Safety Endpoint =’Yes’
ELSE Total Early and Late Onset Composite Safety Endpoint =’No’
- Derived criteria “Total Early Onset Composite Safety Endpoint” will be defined as follows:
IF Death=Yes **OR** Myocardial infarction =Yes **OR** Diaphragmatic Paralysis =Yes **OR** TIA =Yes **OR** CVA=Yes **OR** Major pericarditis =Yes **OR** Tamponade/Perforation =Yes **OR** Heart Block =Yes **OR** New or Prolonged Hospitalization, excl. AF/AFL =Yes **OR** Vascular Access Complication =Yes **THEN** Total Early Onset Composite Safety Endpoint=’Yes’
ELSE Total Early Onset Composite Safety Endpoint=’No’
- Derived criteria “Total Late (any time during follow-up through 12 months)” will be defined as follows:
IF PV Stenosis =Yes **OR** AE fistula =Yes **THEN** Total Late (any time during follow-up through 12 months) =’Yes’
ELSE Total Late (any time during follow-up through 12 months) =’No’.

Secondary Safety endpoint

- Derived criteria “Death 7 days” will be defined as follows:

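### Table 4 counts heart block in the primary safety composite only after an 'inappropriate' ablation, an undefined extra test that can exclude device- or procedure-related AV block

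*Protocol*

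**What the plan says.** Protocol 6.1 restricts the composite to "serious adverse events (SAEs) which are device- or procedure-related, as adjudicated by the CEDMC and defined below in" Table 4. It lists nine early components, counted within 30 days of an index or remap procedure, and two late ones.

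The Table 4 row for heart block reads "Impairment of AV conduction requiring permanent pacing intervention, if resulting from inappropriate ablation application".

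Three other places bear on the row:

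- Protocol 4.1 names "Conduction system injury resulting in sinus arrest or heart block, either transient or permanent, potentially requiring pacemaker insertion" among the possible complications of AF ablation in general and of this system. It sets no condition on how the ablation was applied.
- Protocol 7.7 gives "harm to the subject is due to error in use" as one of the criteria for a causal relationship. Note 2 of 7.3.1 likewise counts events from use error as adverse device effects.
- SAP 2.5 derives the component from the adjudication form, using "PRIMARY SAFETY ENDPOINT EVENT CRITERIA=' Heart Block" as the category. It gives no definition of its own, so Table 4 governs. SAP 2.4.8.1 and SAP Table 8 print only the component's name.

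**The concern.** The attribution question for the composite is already settled by 6.1. The heart-block row then asks a different question: not whether the ablation caused the block, but whether the application was proper. A committee applying the row literally would have to leave out a subject who needs a permanent pacemaker after a correctly delivered study-device application, and count a subject with the same injury after a misapplied one.

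The study's objective is whether the system is a feasible and safe treatment, so losing the first kind of event would take away information the primary safety endpoint exists to give. The test is also hard to apply consistently. The word is undefined, and the protocol leaves repeat applications and additional lesion sites to the investigator's discretion, so there is little protocol standard to judge against. A reader of SAP Table 8 would see only the component name and would not know that the restriction exists.

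**Working it through.** The plan states no figure that depends on this clause, so there is nothing to reproduce. The check is a comparison of texts, followed by an illustration of scale.

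**1. Tests a heart-block event must pass**

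- From 6.1: it is serious, it is device- or procedure-related as adjudicated, and it falls within 30 days of an index or remap procedure.
- From Table 4: AV conduction is impaired, permanent pacing is required, and the block results from an inappropriate ablation application.

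The first two Table 4 tests set the diagnosis and its severity. The third is a further attribution test on top of 6.1.

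**2. The other ten rows of Table 4**

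These rest on clinical, imaging, severity or timing criteria. Tamponade/perforation, for example, is "The development of a significant pericardial effusion during or within 30 days of undergoing the index AF ablation procedure", with haemodynamic, drainage and effusion-size criteria. Two rows do mention cause: diaphragmatic paralysis must not be due to a pulmonary process, and stroke must have a vascular cause. Both clauses identify the condition. Neither asks whether the ablation was properly done.

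**3. The two readings of the clause**

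| Reading of *inappropriate* | Related AV block after a correctly delivered application | Effect of the clause |
|---|---|---|
| Improper or erroneous application | Meets 6.1, fails Table 4 | Event excluded from the CSE |
| Off-target or unintended lesion | Meets 6.1 and Table 4 | Redundant with 6.1 for ablation-caused block |

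On neither reading does the clause add an event to the composite.

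**4. Scale, for illustration only**

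Inputs: up to 40 subjects (Protocol 3.7); two-sided 95% intervals (Protocol 5.1, SAP 2.1.4); one otherwise event-free subject with related AV block needing permanent pacing, judged not inappropriate. The count follows the protocol's definition of the composite, not the SAP's programming of it. When asymptotic assumptions fail, SAP 2.1.4 uses Agresti-Coull at 0% or 100% and the exact interval otherwise.

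With the clause, 0/40:

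- Agresti-Coull: z² = 3.8415; ñ = 40 + 3.8415 = 43.8415; p̃ = (3.8415/2)/43.8415 = 0.0438. Upper limit = 0.0438 + 1.96 × √(0.0438 × 0.9562/43.8415) = 0.0438 + 0.0606 = 10.4%.
- Exact, for comparison: 1 − 0.025^(1/40) = 8.8%.

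Without the clause, 1/40 = 2.5%:

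- Exact lower limit: 1 − 0.975^(1/40) = 0.06%.
- Exact upper limit: 97.5th percentile of Beta(2, 39) = 13.2%.

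Each excluded subject moves the CSE by 1/40 = 2.5 percentage points.

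**5. Chance that it matters**

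The documents give no heart-block rate. For an assumed rate p of events the clause would exclude, the chance of at least one in 40 is 1 − (1 − p)^40:

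- p = 0.5%: 18%
- p = 1%: 33%
- p = 2%: 55%

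**The case against.** The strongest reply is that *inappropriate* need not mean operator error. The protocol has its own term for that, use error (7.5), and Table 4 does not use it. None of the planned lesion sets (pulmonary veins, cavo-tricuspid isthmus, focal or left atrial sites) is aimed at AV conduction. An adjudicator could therefore regard any application that damages it as off-target, and little or nothing would be excluded. The CEDMC Charter (9.10) may settle the meaning, but it is not among the documents. This part stands: the exclusion is a possible consequence of the wording, not an established one.

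It also stands that the event would not vanish. It would count in secondary safety endpoint 2, which SAP 2.5 derives broadly enough to include events unlikely to be related, and it would appear in the SAE tables. The SAP's programmed composite contains "New or Prolonged Hospitalization, excl. AF/AFL =Yes OR Vascular Access Complication =Yes", so its hospitalization component might catch a pacemaker admission. That component is absent from the list in Protocol 6.1 and from SAP Table 8. It is a separate inconsistency and cannot be relied on as a remedy.

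Finally, the study is descriptive, with no hypothesis or required sample size (5.3). That limits the severity.

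None of this is a reason to keep the clause. On the benign reading it adds nothing to 6.1 for ablation-caused block. On the literal reading it removes related harm. Defining the term would end the ambiguity, but a definition in the literal sense would keep the exclusion.

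**Conclusion.** The heart-block row carries an undefined second attribution test that no other component has. Read literally, it can remove device- or procedure-related AV block requiring permanent pacing from the CSE, and any such removal can only make the result look better. One excluded event in 40 otherwise event-free subjects would show as 0/40 (upper limit about 10.4% by the SAP's method) in place of 2.5% (0.06% to 13.2%). This rests on the literal reading, on 40 treated subjects and on an assumed single event; the true number is unknown and probably small.

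A reader might infer that the plan definitely leaves out AV block caused by the device used as intended, and that the primary safety rate is therefore biased. The documents do not support that: the word is undefined, a benign reading is available, and no rate is given. Nor would the event be lost from safety reporting as a whole. The loss would be confined to the primary composite and its 7-day version, which reuses the same definitions. Severity is moderate.

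**What to change.** In Table 4, end the heart-block entry at the comma, deleting the condition that follows it. Attribution then rests on the device- or procedure-relatedness rule in 6.1 alone, as it does for the other components. If the sponsor wants to know whether an application was appropriate, add a field for this to the adjudication form and report it descriptively, with no effect on whether the event counts.

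The text change is one clause, but it alters a primary endpoint definition. It therefore needs the usual amendment approvals and site training (10.3, 10.4), and any heart-block case already adjudicated needs re-review. The CSE may become slightly less favourable. SAP 2.5 needs no change on this point, since it takes the adjudicated category as given.

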6.2 Secondary Safety Endpoints

1. The Primary Safety Endpoint assessed at 7 rather than 30 days
2. The proportion of subjects with a device- or procedure-related SAE
3. The proportion of subjects with stroke or TIA
4. The proportion of subjects requiring cardioversion
5. The proportion of subjects requiring an arrhythmia-related hospitalization

6.3 Primary Feasibility Endpoint

The proportion of subjects that achieve Acute Procedural Success (APS) defined as the percutaneous endocardial creation of a complete, electrically isolating set of lesions around the ostia of the pulmonary veins (PVI) using the FARAPULSE Endocardial Multi Ablation System during the Index Procedure, as clinically assessed by entrance and/or exit block performed \geq 20 minutes after the last PVI lesion is made.

6.4 Secondary Feasibility Endpoints

1. The proportion of subjects who undergo the protocol-specified 75-Day Remapping Procedure and achieve Chronic Procedural Success (CPS) defined as persistent electrical isolation of all initially ablated pulmonary veins. Chronic Procedural Success will be subdivided by Index Procedure only CPS and Reablated CPS subjects.

2. The proportion of attempted subjects that achieve Acute CTI Success, defined as the creation of bi-directional electrical block across the CTI using the investigational devices.
3. Durability of the CTI and/or other extra-PV lesion set(s), when applicable. Durability is defined as unaltered integrity of each such lesion assessed at the Remapping Procedure.
4. The proportion of subjects that achieve Therapeutic Success, defined as freedom from:
 - a. Post-Blanking Period through assessment: occurrence of AF, AFL or AT, or ablation for AF/AFL/AT using the study device
 - b. At any time: ablation for AF/AFL/AT with a nonstudy deviceTherapeutic Success will be assessed from the end of the 90 Day Blanking Period through Months 6 and 12 and will be subdivided by on / off AFDs (Atrial Fibrillation Drugs) post-Blanking Period.

6.5 Additional Assessments

1. Proportion of subjects with early recurrence of atrial fibrillation (ERAF) by 90 days after the initial study ablation.
2. Time to Therapeutic Failure
3. Proportion of all ablated pulmonary veins that are isolated at the Index Procedure using the study device.
4. Proportion of all ablated pulmonary veins isolated using the study device during the Index Procedure that remain isolated at the 75-day Remapping Procedure.
5. The proportion of attempted subjects that achieve Chronic CTI Success, defined as persistent bi-directional electrical block across the CTI as assessed at the 75-day remapping procedure.
6. The proportion of attempted subjects that achieve Chronic Focal Success, defined as persistent electrical nonconductivity of extra-PV tissue targeted for ablation in the Index Procedure, excluding the CTI

6.6 Procedural Assessments

- 1) Assessments of duration for procedure components:
 - a. Procedure time (initiation of venous access to venous access closure)
 - b. Dwell time (sum of catheter entry-to-exit durations for each cardiac chamber)
 - c. Total ablation time (first ablation to last ablation)
 - d. Fluoroscopy time and dose (total duration and dose of exposure)
- 2) Characterization of lesion sets:
 - a. PVI ablations
 - b. Extra-PV ablations, excluding CTI ablations
 - c. CTI ablations
 - d. Anomalous PV ablations

7. Adverse Events, Device Effects, Malfunctions and Deficiencies

7.1 Adverse Events

An Adverse Event (AE) is any untoward medical occurrence, unintended disease or injury, or untoward clinical signs (including abnormal laboratory findings) in subjects, users or other persons, whether or not related to the investigational medical device.

- NOTE 1: This definition includes events related to the investigational medical device or the comparator.
- NOTE 2: This definition includes events related to the procedures involved.
- NOTE 3: For users or other persons, this definition is restricted to events related to investigational medical devices.
- NOTE 4: This definition excludes medical conditions, findings or abnormalities present at the time of enrollment, which are defined as pre-existing conditions. Pre-existing conditions will not be included in the adverse event dataset. However, a worsening of a pre-existing condition during the study does constitute an adverse event.

